We will use propensity score methods to control for potential confounding patient or provider characteristics that may affect the acceptance to enroll in the study and, consequently, the outcome of interest (HIV viral suppression, adherence, and reinitiation). Propensity score methods help us balance the distribution of the covariates between treatment and control groups, reducing the selection bias and allowing for more accurate causal inference when assessing the impact of the treatment. Propensity scores (PS) will be calculated as the predicted probabilities of being in the treatment group. Logistic regression model predicting being in the enrolled in the study will be used. A wide range of patient (age, gender, race, Medicaid enrollment, etc.), provider (specialty), hospital and geographical (region, rurality) characteristics will be considered in the regression model. We will use the PS to match the treatment group to the control group. We will calculate the inverse probability weights (IPW) using these PS. We will evaluate the effect of the program in the PS matched samples on the binary outcomes—including HIV RNA viral load <200 copies/mL (primary outcome), adherence (secondary outcome), and reinitiation (secondary outcome)—by comparing the proportions between the Program arm and the Usual Care arm. We will use Chi-squared tests to evaluate the statistical significance of the effects of treatments on proportions. We will also use logistic regression models to test for the program effects, adjusting for all potential confounders that might affect the outcome and bias the results.

Sample size and statistical power considerations

We expect to enroll 100 participants in the Program arm. This sample size provides adequate power to detect differences in HIV viral suppression (i.e., HIV viral load <200 copies/mL), the primary outcome, across arms. Assuming a 50% rate of viral suppression in the control group, with 100 subjects in the control group, we will be able to detect a difference of .28 in the rate of viral suppression with greater than 80% power. This requires a sample size of 350 participants in each arm. However, an estimated 30% of the sample will be missing HIV viral load data (Crepaz et al. *MMWR Morb Mortal Wkly Rep* 2018). This translates into dropping the power to 70%. According to our experience with these data, and the

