inclusion and Virginia Medicaid–Virginia Department of Health matching protocols, we note that no missing data are allowed.

Other data and analyses

Other data to be collected through interactions with participants include the quality improvement initiative's process data. These data will be used to track study progress and facilitate recruitment and enrollment (e.g., number and timing of contact attempts, mailing address for optional certified letter), current ART use to determine final eligibility (i.e., confirmation that the participant has not refilled their ART prescription), and barriers discussed and referrals made.

Additionally, PositiveLinks app metadata and usage data will be collected through the PositiveLinks app. App metadata include: number of app launches, number of app log ins, response rates for daily queries about medication, response rates for daily queries about mood, response rates for daily queries about stress, response rates for weekly quizzes, number of posts to community message board, number of direct messages to linkage coordinator, and number of times visiting resources section. The text of community board posts will also be collected.

Descriptive statistics will be used to summarize recruitment and enrollment, barriers endorsed, referrals made, and PositiveLinks app usage. We may examine correlates of these variables and/or consider these variables as confounders in the primary evaluation analyses. Community board posts from the PositiveLinks app will be examined using textual analysis methods.

Data management

Data management and statistical analysis will be performed using Terradata 16.10, REDCap 10.9.4, and SAS® Software version 9.4 (or most recent VCU- and agency-approved software releases available). Statistical analysis will occur at Virginia Medicaid, Virginia Department of Health, VCU, University of Virginia, and CDC. Intermediate datasets will be stored on Virginia Medicaid servers, Virginia Department of Health servers, and University of Virginia servers. Final limited and de-identified datasets will be stored at Virginia Medicaid, as well as Virginia Department of Health, and also securely transferred to VCU and CDC.

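### The sample-size paragraph contradicts itself: neither 350 per arm nor 70% power follows from its own inputs, and it assumes both 30% missing viral loads and none

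*Combined protocol and SAP*

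**What the plan says.** Everything on this point is in the section headed Sample size and statistical power considerations. In order, the paragraph states:

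1. The planned size: "We expect to enroll 100 participants in the Program arm".
2. That this is enough: "This sample size provides adequate power to detect differences in HIV viral suppression".
3. The inputs: a 50% control suppression rate and, "with 100 subjects in the control group, we will be able to detect a difference of .28", with power above 80%.
4. The requirement: "This requires a sample size of 350 participants in each arm".
5. Incomplete outcome data: "an estimated 30% of the sample will be missing HIV viral load data".
6. The consequence: "This translates into dropping the power to 70" per cent.
7. The closing position, which appeals to experience with the data and to the inclusion and matching protocols: "we note that no missing data are allowed".

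The Statistical analysis section names a chi-squared test comparing proportions in the propensity-score-matched samples. No significance level or sidedness is given anywhere. A 1:1 ratio is implied by 100 and 100 but is not stated as the matching ratio.

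**The concern.** Items 1 to 3 say that 100 per arm is enough for a 0.28 difference. Item 4 says that the same objective takes 350 per arm, 3.5 times as many. Items 5 and 6 assume that 30% of primary outcomes are missing and report inadequate power as a result, while item 7 says that none will be missing.

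This is the only sample-size justification in the document. Taken at face value, 350 implies a shortfall of 250 per arm and 70% implies a primary analysis below the usual 80%. A reader judging whether a null result is informative would be misled if neither follows from the inputs. The paragraph is also the only place in the statistical sections that deals with missing viral loads, so the contradiction leaves the evaluable number for the primary outcome undefined.

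**Working it through.** **Inputs from the plan.** Control proportion p1 = 0.50; difference 0.28, so p2 = 0.78; 100 per arm; 30% missing, which leaves 100 × 0.70 = 70 per arm; chi-squared test on two proportions.

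**Assumptions not in the plan.** Two-sided alpha 0.05 (z = 1.960), 1:1 allocation, unadjusted and unweighted test. For 80% power, z = 0.842.

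**Formulas** (pooled-variance normal approximation, with p̄ = (0.50 + 0.78)/2 = 0.64):

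- A = √[2 p̄(1 − p̄)] = √(2 × 0.64 × 0.36) = 0.6788
- B = √[p1(1 − p1) + p2(1 − p2)] = √(0.2500 + 0.1716) = 0.6493
- n per arm = [(1.960 A + 0.842 B)/0.28]²
- power = Φ[(0.28√n − 1.960 A)/B]

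**Step 1: the claim of more than 80% power at 100 per arm.** (0.28 × 10 − 1.960 × 0.6788)/0.6493 = 2.263, so power is 98.8%. The claim is true as a lower bound. Exact enumeration also gives 98.8%.

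**Step 2: the stated requirement of 350 per arm.** [(1.3305 + 0.5465)/0.28]² = 44.9, so 45 per arm. The stated 350 is 350/45 = 7.8 times this. With continuity correction the requirement is 52. With 45 inflated for 30% loss it is 45/0.70 = 64.3, so 65.

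**Step 3: the stated 70% power after 30% loss.** At 70 per arm: (0.28 × 8.367 − 1.3305)/0.6493 = 1.559, so power is 94.0% (exact enumeration 94.0%; with continuity correction 91.5%). Starting from 350 per arm does not give 70% either: 30% loss leaves 245, where power for 0.28 exceeds 99.9%.

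**Step 4: sensitivity to the assumed alpha.**

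| Two-sided alpha | n per arm for 80% power | Power at 70 per arm |
|---|---|---|
| 0.10 (same as one-sided 0.05) | 36 | 97.1% |
| 0.05 | 45 | 94.0% |
| 0.01 | 68 | 82.0% |

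No row comes near 350 or 70%. Two other readings of 0.28 also fail to give 350: as Cohen's h it needs about 200 per arm, and as a relative increase (50% to 64%) it needs 196.

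**Step 5: what each size can detect with 80% power.** A difference of 0.193 with 100 per arm, 0.229 with 70 and 0.105 with 350.

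**Step 6: possible origin, not confirmed by the documents.** If 100 were the total, 50 per arm gives 84.1% power for 0.28, falling to 69.2% at 35 per arm. That fits 0.28, above 80% and about 70%, but the text gives 100 for each arm. Alternatively, 350 per arm with a difference of 0.11 gives 83.5%, falling to 68.9% at 245; the value 0.11 was chosen to fit. The paragraph may combine more than one calculation.

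**Step 7: the missing-data statements.** The Screening section requires a record in the HIV surveillance data. It does not require a viral load result, and so not one at 3-month follow-up. The inclusion and matching rules therefore do not by themselves guarantee a complete primary outcome.

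**The case against.** The strongest defence is that the operative claim is correct: 100 per arm does give more than 80% power for 0.28. The planned enrolment is stated directly, and 350 is called a requirement, never an enrolment target. No analysis or decision rule uses 350 or 70%, and both wrong figures make the design look weaker than it is. The missing-data sentences can also be read as a sequence, in which an external 30% estimate is quoted and then overridden by the study's own experience. Finally, a conservative power statement is reasonable when propensity matching or weighting may cost precision.

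Much of this stands. The intended number is 100, there is no evidence of underpowering for 0.28, and a lower bound of 80% is not an error. It does not rescue the paragraph. A stated sample size and a stated power are both wrong on the plan's own inputs. The override reading still leaves the 30% and 70% sentences standing beside their denial, and the eligibility rules cited in support do not require a follow-up viral load. The paragraph makes no allowance for matching or weighting. If a 20% loss of effective sample size is assumed for illustration, 70 per arm becomes 56 and power is 88.1%, still well above 70%.

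**Conclusion.** The concern holds. For a 0.28 difference from 50%, about 45 per arm give 80% power, against 350 stated. Power after 30% loss is 94.0%, against 70% stated, and with complete data it is 98.8%. These figures assume a two-sided 0.05 unadjusted test with equal arms. The conclusion does not depend on that choice across alpha 0.01 to 0.10 or on continuity correction. The statements of 30% missing and none missing are not reconciled. The consequence is an unusable justification and an undefined evaluable number, not a demonstrated shortage of participants. It must be corrected because it is the plan's only basis for its size.

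**What to change.** First identify which calculation was intended. Unless 350 per arm and 70% come from a separate calculation, remove both; if they do, state its inputs and keep it apart. State alpha, sidedness and the matching ratio. State one assumption about missing viral loads. If only people with a follow-up result are analysed, say so and give the expected evaluable number.

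If 100 per arm, 1:1 and two-sided 0.05 are confirmed, suggested text is:

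> With 100 participants per arm, control suppression of 50% and a two-sided 0.05 chi-squared test, the study has 80% power to detect a difference of about 0.19 (0.193) and about 99% power for 0.28. [If 30% missing applies: with 70 evaluable per arm, about 0.23 and 94%.] These figures ignore any loss of effective sample size from propensity score matching or weighting.

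The cost is redrafting one paragraph and stating the design inputs. Enrolment and data collection are unchanged.

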We will exclude enrollees who have a record of third-party health insurance during the past 3 months. We will exclude enrollees who have a missing phone number and/or mailing address. We will exclude those experiencing within-class ART switches due to medication toxicity (defined as a new within-antiretroviral class ART prescription claim >30 days of the expected date of ART prescription refill or renewal). We will also exclude those enrollees experiencing ART resistance and thus switching to a new regimen (defined as a claim for an antiretroviral drug in a new ART class occurring >30 days of the expected date of ART prescription refill or renewal). We will exclude enrollees whose linked HIV provider is a provider practicing at a facility offering PositiveLinks. The study will exclude enrollees who do not have a record in Virginia’s HIV surveillance data, as a record in the HIV surveillance data confirms HIV status. The study will exclude enrollees who do have a record of an ART prescription(s) in the Virginia HIV surveillance data, but did not have a record of an ART prescription(s) in the claims data, as an additional confirmatory check on study eligibility. We will exclude enrollees who do not speak English, as PositiveLinks has not been validated in languages other than English.

An initial database of eligible potential participants will be constructed and include: first and last name, social security number, complete or partial address, race/ethnicity, sex at birth, and date of birth; and expected date of ART prescription fill, refill, or renewal; and an indicator for a late ART prescription refill(s) by >30–365 days). Analysis will be conducted by authorized VCU personnel and saved on the Virginia Medicaid servers per an amendment to an existing Interagency Agreement between Virginia Medicaid and VCU.

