Overview. Patient-level support in the program arm seeks to improve timely filling of ART prescriptions among participants with late ART prescription refill(s) by >30–365 days. The program arm will consist of up to two phases, which will be distinguished by the barriers primarily addressed in each phase. Both phases will involve phone consultations to discuss barriers to prescription adherence. Both phases also will provide referrals to resources that address participant barriers to timely filling of ART prescriptions. However, discussion with participants whose ART prescriptions fills have been late for a more extended period (>60 days) will focus on more complex barriers to filling ART prescriptions (e.g., substance use, unstable housing) and these participants will be additionally offered PositiveLinks, a warm health technology support to promote better health for people living with HIV. The phone consultations will be delivered by a linkage coordinator.

Patient-level support in the program arm will involve: 1) Screening, recruitment of eligible potential participants, 2) Informed consent, 3) Courtesy notification letter and study information sheet for providers, 4) Program implementation, and 5) Follow-up.

Screening, recruitment, and arm assignment. Screening and recruitment will occur as described previously.

Informed consent. Informed consent procedures will be conducted verbally by the linkage coordinator and follow identity verification. Informed consent will occur via phone at a time that is convenient for the eligible potential participant. Thus, informed consent may occur immediately following identity verification or at subsequently scheduled time. The complete informed consent process will precede program implementation. Subsequent telephone contact will involve reminders that participants may withdraw from the study at any time and for any reason without penalty; they will also involve opportunity for questions.

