Phase 1. Phase 1 is for participants with late ART prescription refill(s) by >30–60 days. The phone consultation will involve a 30-minute discussion of the participant’s barriers to filling their ART prescription and referrals to resources that may address these barriers. The consultation will use a conversational format guided by scripted prompts. During the consultation, the linkage coordinator will document data on each participant’s self-reported barriers to filling ART prescriptions. Referrals will be made to existing resources that are already offered through the participant’s Medicaid managed care organization or through pharmacists, their HIV provider, or local community resources. If a participant self-reports multiple barriers to filling ART prescriptions, the participant will be asked to prioritize the barriers; this will allow the linkage coordinator to provide referral information that aligns most closely with participant preferences. Whenever possible, the primary referral will involve a warm hand-off, where the linkage coordinator introduces the participant directly to the referral resource in real-time. This approach is designed to engage the participant and maximize success in the referral process. If a warm hand-off is not possible at the time of the consultation, a follow-up call can be scheduled to make the warm hand-off; referral contact information will be offered to the participant after 3 unsuccessful warm hand-off attempts. Participants will additionally be given contact information for referrals involving 1-2 other prioritized barriers. The referral resource, referral date, and referral time will be documented by the linkage coordinator. Approximately ten business days after the Phase 1 referral, the participant’s ART prescription claims will be followed in the Medicaid claims data. The 10-business-day threshold will allow adequate time for an ART prescription fill and prescription claim reimbursement. If the participant has an ART prescription claim after this 10-business-day period, the participant will not be contacted further. If the participant has no ART prescription claim after the 10-business-day period, the participant will be eligible for Phase 2.

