Phase 2. Phase 2 is for participants with late ART prescription refill(s) by >60 days. Phase 2 will involve a more intensive phone consultation, in which more complex barriers may be assessed. Three phone contact attempts will be made in the same manner as in Phase 1. Participants who do not respond to these contact attempts, who do not verify their identities, or who do not either consent to participate or assent to continue to participate will not be contacted further. The linkage coordinator will guide a 30-minute consultation similar in format to Phase 1. In Phase 2, however, more complex barriers, such as substance use and mental health concerns, will be probed and referrals made accordingly. Participants in Phase 2 will also be offered PositiveLinks, an evidence-based mobile app designed to support ART adherence and retention in care (<https://www.positivelinks4ric.com/>). PositiveLinks is based on theories of behavior change and provides 1) daily check-ins on mood, stress, and medication adherence, which promote self-monitoring; 2) educational resources for users; 3) direct messaging with study linkage coordinators; 4) an anonymous message board to connect with peers living with HIV to provide and receive social support; and 5) contact information for patients’ providers and pharmacies. A major strength of the app is its support of self-monitoring, which addresses intrapersonal barriers to ART adherence. The app contains data security measures designed to protect patient privacy and confidentiality (e.g., phone calls to providers made through the app do not appear in the phone’s call log). Further details on the app’s development, user functions, and security features are available in the uploaded supporting documents. We emphasize that all study participants will be enrolled in Virginia Medicaid, and contracted Medicaid managed care organizations provide smartphones for enrollees (see

<https://www.virginiamanagedcare.com/choose/compare-plans>); therefore, we do not anticipate that smartphone ownership will be a barrier to participants' enrolling in PositiveLinks.

Follow-up. A 3-month follow-up period will begin on the date of the final consultation (**Table 1**).

Table 1. Start date of 3-month follow-up for participants receiving patient-level support

Phase(s) received	Start of 3-month follow-up
Phase 1 only	Date of final phase 1 consultation
Phase 2 only	Date of final phase 2 consultation

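### The plan allows program-arm process variables (referrals, app use, contact attempts, consultation-recorded barriers) to be treated as confounders in the program versus usual care comparison, where they cannot play that role

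*Combined protocol and SAP*

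**What the plan says.** The section Other data and analyses introduces process data as "Other data to be collected through interactions with participants". It lists contact attempts, current ART use to settle eligibility, barriers and referrals, and then app data such as "response rates for daily queries about medication". After stating that recruitment and enrollment, barriers, referrals and app use will be summarised, it adds: "We may examine correlates of these variables and/or consider these variables as confounders in the primary evaluation analyses".

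Four other parts of the document bear on this.

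- **Program content.** Procedures: Program arm says "Both phases also will provide referrals to resources that address participant barriers to timely filling of ART prescriptions", and under Phase 2, "Participants in Phase 2 will also be offered PositiveLinks". Under Phase 1 the linkage coordinator documents "self-reported barriers to filling ART prescriptions".
- **Refill rule.** Under Phase 1: "If the participant has an ART prescription claim after this 10-business-day period, the participant will not be contacted further".
- **Controls.** Procedures: Usual care arm rules out any contact and any study intervention, and uses only existing secondary data, de-identified and without a code key. Recruitment states that it applies to the program arm only. Screening adds: "We will exclude enrollees whose linked HIV provider is a provider practicing at a facility offering PositiveLinks".
- **Analysis.** Statistical analysis builds the propensity score from patient, provider, hospital and geographical characteristics, compares proportions in the matched sample by chi-squared test, and also fits logistic models that adjust for every potential confounder, with no closed list and no timing rule.

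**The concern.** A confounder has to be comparable in both arms and must not be a consequence or a component of the treatment. The variables named here fail that test in different ways. The arms are not randomised, so the choice of covariates carries the causal claim. An open option to add treatment components to the adjusted model can also be taken up after the results are known. The arm coefficient would then no longer estimate program versus usual care, although it would probably still be reported as the adjusted program effect.

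**Working it through.** The plan gives no figure for this point, so the check is first a reading of each variable and then an illustration.

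**1. Each variable in each arm**

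| Variable | Program arm | Controls | Consequence of adjusting |
|---|---|---|---|
| Referrals | Delivered in both phases | Zero by design | Conditions on the program |
| PositiveLinks use | Offered in Phase 2 | Zero by design | Conditions on the program and on earlier refilling |
| Contact attempts | Generated by recruitment and follow-up calls | Zero by design | Cannot be balanced across arms |
| Barriers | Self-reported in the consultation | Unmeasured, not obtainable later | Cannot be adjusted for between arms |

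App use has a further fault. A Phase 1 participant who refills is not contacted again, and the app belongs to Phase 2. App use is therefore zero by rule for Phase 1 refillers, and refilling is itself the secondary outcome of reinitiation in the Outcomes section.

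**2. What the software would do**

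- App use with controls coded 0: the model fits without an error.
- A yes/no referral indicator, if every program participant has a referral and no control does: it equals arm. The design matrix (intercept, arm, referral) has rank 2 of 3, and the effect is not estimable.
- Barriers: if blanks are stored as missing, a complete-case fit drops every control. If blanks are coded 0, the model runs silently.

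**3. Size when app use is adjusted for (illustration)**

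Inputs from Sample size and statistical power considerations: control rate 0.50 and difference 0.28, so the program rate is 0.78. The unadjusted odds ratio is (0.78/0.22)/(0.50/0.50) = 3.55.

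Assumptions not in the documents: a share m of the effect passes through the app, a fraction u of the program arm uses it, use is coded yes/no, and use is unrelated to prognosis.

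- Non-user rate = 0.50 + (1 − m) × 0.28
- User rate = non-user rate + m × 0.28/u, which keeps the arm average at 0.78

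All controls are non-users, so the adjusted arm term compares program non-users with controls, and u drops out.

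| m | Non-user rate | Difference left | Odds ratio |
|---|---|---|---|
| 0 | 0.78 | 0.28 | 3.55 |
| 0.5 | 0.64 | 0.14 | (0.64/0.36)/1 = 1.78 |
| 1 | 0.50 | 0 | 1.00 |

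The last row needs u of at least 0.28/0.50 = 0.56, so that the user rate does not exceed 1.

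**4. Direction through the refill rule (illustration)**

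Suppose neither the program nor the app has any effect, so the program-arm rate is 0.50. Assume 25% of the arm refills after Phase 1, 70% of these are suppressed, and 60% of the rest use the app.

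- Rate in the rest: (0.50 − 0.25 × 0.70)/0.75 = 0.433.
- If users and non-users in the rest have the same prognosis, the rate among all non-users is (0.175 + 0.75 × 0.40 × 0.433)/(0.25 + 0.30) = 0.305/0.55 = 0.555. The arm term is +0.055 (odds ratio 1.24) when the truth is 0.
- If users in the rest do 20 points better for reasons of prognosis, non-users in the rest have 0.433 − 0.60 × 0.20 = 0.313. The rate among all non-users is (0.175 + 0.30 × 0.313)/0.55 = 0.489, and the arm term is −0.011.

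The sign changes with an assumption that the documents do not settle.

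**The case against.** The strongest defence is that nothing commits the analyst to this error. The sentence is permissive. The propensity covariates named in Statistical analysis include no process variable, and the matched chi-squared comparison does not use these data at all. That stands and limits the reach. A reader might infer that the matched comparison or the inverse probability weights are already compromised; the documents do not support this, because both are affected only if these variables are added to the propensity model. The exposure is mainly the additional logistic model with its open list of confounders.

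A second defence is that barriers such as unstable housing or substance use may well be real confounders. They may. But the plan records them in one arm only, and a variable unmeasured in every control cannot be adjusted for between arms, however prognostic it is.

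Third, it is tempting to say that nothing in the recruitment and enrollment data could be a valid covariate. That goes too far: screening is monthly and also covers controls, so calendar timing of eligibility exists in both arms. Summarising the process variables and studying their correlates within the program arm is also unobjectionable.

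**Conclusion.** The point holds as a fault in a stated option, not in a committed analysis. Nothing elsewhere in the document withdraws the option, and for referrals, app use, contact attempts and consultation-recorded barriers its use would not give a valid program effect. That conclusion is structural and needs no numbers.

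On size, adjusting for yes/no app use would leave 0.14 of the planned 0.28 if half the effect passes through the app, and none of it if all does. Both figures rest on an assumed mediated share and on use being unrelated to prognosis. A reader might infer that the bias always runs toward no effect; the refill rule does not support that, since it can push the estimate up or down. The bias cannot be signed in advance. Nor can one rely on the mistake showing itself: a referral indicator equal to arm would fail visibly, but app use, or barriers with blanks coded 0, would not.

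**What to change.** Replace the sentence that offers these variables as confounders with:

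> Contact-attempt, consultation-recorded barrier, referral and app-use variables will be summarised, and their correlates examined, within the program arm only. They will not be used as confounders in the propensity model or in the logistic models that estimate the program effect; those models will use only covariates ascertained in the same way in both arms (e.g. from claims or surveillance data) on or before the date of first confirmed eligibility.

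The words 'on or before' matter: days late is established when eligibility is confirmed, and a strict 'before' could shut out a likely prognostic factor. Days late at eligibility and calendar month of eligibility remain allowed, as does a separately labelled exploratory mediation analysis.

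The cost is one sentence and no new data collection. Because screening repeats monthly and recruitment can span months, the date of first confirmed eligibility must be kept for each program participant. Procedures: Usual care arm already uses that date for controls.
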